**A Pilot “Window of Opportunity” Neoadjuvant Study of Propranolol in Breast Cancer**  
**Principal Investigator: [name]**  
**Co-Principal Investigator: [name], MBA**

conserving surgery

D) Medically able to abstain from alcohol and all illicit drugs, and limit caffeine intake to less than or equal to 2 cups of coffee per day for at least two weeks before and during the treatment period.

E) Potential subjects systolic blood pressure must be >90 mmHg and/or diastolic > 50 mmHg and no more than 95 mmHg.

F) Able to read, understand and sign a consent form

G) Normal baseline EKG

Exclusion criteria: - patients will be excluded for any of the following criteria:

A) Pregnancy; potential subjects of female bearing age will have to complete a pregnancy test during screening to ensure that they are not pregnant. Potential patients who are post-menopausal must have confirmed one year without menstrual cycle.

B) Free of major medical illnesses including:

- Cardiac diseases (history of cardiac valve disease, coronary artery disease, congestive heart failure, A-V block, peripheral vascular disease, any cardiac arrhythmia/bradycardia) with the exception of the diagnosed cancer.

C) Histories of asthma, bronchospastic disease, or obstructive pulmonary disease

E) Previously diagnosed thyrotoxicosis

F) Severe allergic reactions to medications which are included in the beta blocker family

G) Currently treated with a beta adrenergic receptor antagonist

H) Patients with breast cancer not amenable to surgical resection

I) Patients taking any of the following medications will be excluded:

Input

- Drugs that are categorized as beta-blockers
- Amiodarone
- Sotalol

J) If patient is scheduled to receive surgery in less than 3 weeks of biopsy, then patient will not be eligible.

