### **6. Investigational Plan**

This pilot study is looking to enroll 30 patients total at Texas Tech University Health Sciences Center.

- Once a patient is deemed eligible by the criteria listed above and they sign an informed consent, study treatment will begin. Since we are utilizing the window of opportunity method, it is imperative that we catch patients in the 3 week window from when the patient is diagnosed with breast cancer to when the surgery is scheduled to remove the cancer.
- Participants will remain on 1.5 mg/kg/day of Propranolol, which will be taken twice daily, for 2 weeks and 4 days. The patient will be asked to start a tapering period on day 5 of week 2 and their dose will be lowered by 50%. On day one of week 3, patients will be asked to lower their dose again by 25% of their original dose and they will take the medication at this dose for 4 days. After day 4, the patient will no longer take the medication.[11].
- Patient’s first dose will be in the morning the day after the study medication is distributed to them so that it allows study staff to contact the patient 4-6 hours after they are scheduled to start taking the medication in order to assess toxicities.
- All data points that will be collected will be entered in to the database REDCap.
- All patient visits will be completed at the Garber Breast Care Center at the Texas Tech University Health Sciences Center.

Once a patient signs the appropriate consent and is enrolled in the study, treatment will begin. [name] lab will collect a sample of the biopsied mass and his lab will complete the biomarker assessment on the tissue. Ki-67 assessment is routinely done at the Pathology Department. The baseline study visit will include a physical exam, vitals, electrocardiogram and Eastern Cooperative Oncology Group (ECOG) performance assessment which will be completed by study staff. The subject will be administered the study drug, propranolol. The subject will also receive detailed instructions on how to self-administer the propranolol and be given a medication diary so that they can keep track of when they take the medication. The subject will be provided a blood pressure monitor with a pulse feature included in order to take their blood pressure and pulse twice daily while they are enrolled on the study. When patients are supplied the blood pressure machine

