**A Pilot “Window of Opportunity” Neoadjuvant Study of Propranolol in Breast Cancer**  
**Principal Investigator: [name]**  
**Co-Principal Investigator: [name], MBA**

by study staff, a detailed training of how to use the machines will be provided to the patient. This will be overseen by [name] and a training log will be kept for each patient. Additional training will be provided during the follow-up visits upon patient's request. Study staff will also conduct a chart review to gather the patient's medical history.

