**Contradictions**

## A Pilot “Window of Opportunity” Neoadjuvant Study of Propranolol in Breast Cancer

Principal Investigator: [name]

Co-Principal Investigator: [name], MBA

Propranolol is contraindicated in 1) cardiogenic shock; 2) sinus bradycardia and greater than first degree block; 3) bronchial asthma; and 4) in patients with known hypersensitivity to propranolol hydrochloride.

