### Adverse Reactions

The following adverse events were observed and have been reported in patients using propranolol.

Cardiovascular: Bradycardia; congestive heart failure; intensification of AV block; hypotension; paresthesia of hands; thrombocytopenic purpura; arterial insufficiency, usually of the Raynaud type.

Central Nervous System: Light-headedness, mental depression manifested by insomnia, lassitude, weakness, fatigue; catatonia; visual disturbances; hallucinations; vivid dreams; an acute reversible syndrome characterized by disorientation for time and place, short-term memory

loss, emotional lability, slightly clouded sensorium, and decreased performance on neuropsychometrics. For immediate-release formulations, fatigue, lethargy, and vivid dreams appear dose-related.

Gastrointestinal: Nausea, vomiting, epigastric distress, abdominal cramping, diarrhea, constipation, mesenteric arterial thrombosis, ischemic colitis.

Allergic: Hypersensitivity reactions, including anaphylactic/anaphylactoid reactions, pharyngitis and agranulocytosis; erythematous rash, fever combined with aching and sore throat; laryngospasm, and respiratory distress.

Respiratory: Bronchospasm.

Hematologic: Agranulocytosis, nonthrombocytopenic purpura, thrombocytopenic purpura.

Autoimmune Systemic Autoimmune: Systemic lupus erythematosus (SLE).

Skin and mucous membranes: Stevens - Johnson syndrome, toxic epidermal necrolysis, dry eyes, exfoliative dermatitis, erythema multiforme, urticaria, alopecia, SLE-like reactions, and psoriasisiform rashes. Oculomucocutaneous syndromes involving the skin, serous membranes and conjunctivae reported for a beta blocker (practolol) have not been associated with propranolol.

Genitourinary: Male impotence; Peyronie's disease.

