**A Pilot “Window of Opportunity” Neoadjuvant Study of Propranolol in Breast Cancer**  
**Principal Investigator: [name]**  
**Co-Principal Investigator: [name], MBA**

who will determine any abnormality that would preclude participation. Patients with a normal EKG will be allowed to participate on this trial. After taking the initial dose of propranolol, the study staff will contact the study participant via phone within 4-6 hours in order to follow-up and determine if the patient is having any side effects from the medication. If the patient is found to have side effects, the study staff that conducts the call will immediately notify the PI and/or co-investigators. They will then determine if the study treatment should continue or if the patient should stop treatment. Patients will also be asked to call the study coordinator at any time during the study if they have any further side effects.

In addition to in-clinic assessments, blood pressure and pulse monitoring will be performed and recorded by the participants in-home on a daily basis, twice daily, using supplied monitors to ensure that propranolol is not adversely affecting their blood pressure levels or pulse below established threshold levels. If the blood pressure of any participant drops below 100/60 and/or pulse is <55, propranolol will be stopped and the patient taken off protocol. The event will be counted as an adverse event.

A board certified cardiologist ([name]) who is on active staff at UMC and Texas Tech University Health Sciences Center will review the history and physical exam data, and the EKG to assure that the patient is unlikely to have pre-existing cardiac disease. The cardiologist will also be available throughout the study in order to see patients as needed if the PI and sub-investigators determine it would be beneficial to the patient.

All toxicities will be graded according to CTCAE 4.0. The dose of Propranolol will not be modified. If a patient is found to have an AE grade of 2 or more, treatment will stop and the patient will complete the end of treatment visit.

Study treatment will continue 25 days until there is an unacceptable toxicity, the subject is non-compliant with trial procedures or if the principal investigator and co-investigators feel that it is unsafe for the patient to continue with the treatment.

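### Exclusion F bars only severe allergic reactions to beta-blockers, while the protocol's own drug section contraindicates propranolol in any known hypersensitivity to it (minor safety inconsistency)

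*Combined protocol and SAP*

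**What the plan says.** Section 5 (Eligibility Criteria) has one exclusion that concerns allergy: "F) Severe allergic reactions to medications which are included in the beta blocker family". It covers the whole drug class but applies only to severe reactions.

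Section 7 (Drug Information), in its list of contraindications, says that propranolol must not be given "in patients with known hypersensitivity to propranolol hydrochloride". No degree of severity is attached.

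The Adverse Reactions part of Section 7 shows how wide hypersensitivity to this drug can be: "Allergic: Hypersensitivity reactions, including anaphylactic/anaphylactoid reactions, pharyngitis and agranulocytosis; erythematous rash, fever combined with aching and sore throat". That list runs from anaphylaxis to reactions that need not be severe.

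Section 6 (Investigational Plan) ties treatment to the Section 5 list: "Once a patient is deemed eligible by the criteria listed above and they sign an informed consent, study treatment will begin".

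**The concern.** The two sections set different thresholds for the same risk. Someone with a known, non-severe hypersensitivity to propranolol is contraindicated under Section 7 but not excluded under Section 5. Because Section 6 starts treatment once Section 5 is met and consent is signed, staff who follow the eligibility list literally could dose a patient whom the drug section says not to dose.

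What is at stake is participant safety in rare cases. Participants take propranolol so that its biological effect before surgery can be studied, not for a labelled indication, so there is little benefit to set against giving it to someone with a contraindication. The primary endpoint, the power and the analysis are not touched.

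**Working it through.** The plan gives no figure to reproduce. The check is mainly a comparison of texts, followed by a short calculation of how rare the situation is.

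**Step 1. Compare the two rules.**

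| Patient's known history | Exclusion F (Section 5) | Contraindication (Section 7) |
|---|---|---|
| Severe reaction to propranolol | Excluded | Contraindicated |
| Non-severe reaction to propranolol | Not excluded | Contraindicated |
| Severe reaction to another beta-blocker | Excluded | Not addressed |
| Non-severe reaction to another beta-blocker | Not excluded | Not addressed |

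F is wider than Section 7 by drug and narrower by severity. The only conflict is in the second row.

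**Step 2. Compare with the other contraindications.** Section 7 also names sinus bradycardia, heart block above first degree, and bronchial asthma. Section 5 takes up bradycardia and A-V block in exclusion B and asthma in exclusion C, with no severity qualifier. Hypersensitivity is the one that Section 5 takes up with a severity limit, and the protocol gives no reason for this.

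**Step 3. Look for another safeguard before the first dose.**

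- Exclusion G concerns patients "Currently treated with a beta adrenergic receptor antagonist", and exclusion I lists current beta-blockers, amiodarone and sotalol. Neither covers a past reaction.
- The cardiologist's review in Section 8 is meant "to assure that the patient is unlikely to have pre-existing cardiac disease". It is not aimed at drug allergy.
- Section 6 states: "Study staff will also conduct a chart review". This may bring a past reaction to light, but F as worded would not then exclude the patient.
- The telephone call 4 to 6 hours after the first dose and the rule to stop at an adverse event of grade 2 or more (both Section 8) act only after dosing.

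None of these closes the gap.

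**Step 4. Size.** Inputs:

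- n = 30 patients enrolled (Sections 6 and 9).
- p = share of otherwise eligible candidates with a known non-severe propranolol hypersensitivity. The documents do not give p, so it is treated as unknown.

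If nobody acts on the Section 7 contraindication, the chance of enrolling at least one such patient is 1 − (1 − p)^30, and the expected number is 30p.

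Break-even values, from p = 1 − (1 − t)^(1/30):

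- t = 0.05: p = 1 − 0.95^(1/30) = 0.00171, about 0.17% or 1 in 585.
- t = 0.50: p = 1 − 0.50^(1/30) = 0.0228, about 2.3% or 1 in 44.

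Illustrative range (an assumption):

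- p = 0.0005: expected number 30 × 0.0005 = 0.015; chance of at least one 1 − 0.9995^30 = 0.015 (1.5%).
- p = 0.005: expected number 30 × 0.005 = 0.15; chance of at least one 1 − 0.995^30 = 0.140 (14%).

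**The case against.** The strongest reply is that the two sections complement each other. F gives one reason to exclude; it does not instruct anyone to treat milder reactors. The contraindication stands in the same protocol, and a clinician who reads both would withhold the drug. The exclusion list is also loosely drafted: exclusion B, taken literally, would exclude patients who are free of cardiac disease. On this view the list should be read for its intent, which is to keep out patients allergic to beta-blockers. Further, the exclusion letters jump from C to E, so a criterion D may have been lost when the text was read from PDF. Finally, the assumed prevalence has no source in the documents.

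Much of this stands as a limit on the point. An investigator could decline to treat on the strength of Section 7, so for any assumed prevalence the probabilities above are upper bounds. A lost criterion D cannot be ruled out, although nothing indicates that it concerned allergy. The prevalence range is illustrative only.

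It does not remove the inconsistency. Section 6 makes the Section 5 list the condition for starting treatment, and eligibility wording should not depend on staff overriding it from a drug-information section. Reading for intent does not settle the matter either, because the word severe states a threshold that Section 7 does not have.

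**Conclusion.** The concern holds as a minor participant-safety inconsistency. As written, exclusion F admits a patient with a known non-severe hypersensitivity to propranolol, whom Section 7 contraindicates, and no other listed criterion or pre-dose check excludes her.

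The situation is rare: over the assumed range, well under one such patient is expected among 30. These figures measure enrolment of a contraindicated patient, not harm. The conclusion rests on the exclusion list as it appears in the available text and on F being applied as worded.

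**What to change.** Reword exclusion F to: *Known hypersensitivity or allergic reaction of any severity to propranolol, or severe allergic reaction to any other beta-blocker.*

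This brings F into line with the Section 7 contraindication and keeps the present threshold for the rest of the class. It is a one-line eligibility edit. Its only cost is the occasional loss of an otherwise eligible patient with a known non-severe propranolol reaction, about 0.015 to 0.15 per 30 on the assumed range. The sample size and analysis do not change.

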### Cardiovascular Drugs:

Antiarrhythmics - The AUC of propafenone is increased by more than 200% by co-administration of propranolol. The metabolism of propranolol is reduced by co-administration of quinidine, leading to a two-three fold increased blood concentration and greater degrees of clinical beta-blockade.

The metabolism of lidocaine is inhibited by co-administration of propranolol, resulting in a 25% increase in lidocaine concentrations.

Calcium Channel Blockers - The mean Cmax and AUC of propranolol are increased, respectively, by 50% and 30% by co-administration of nisoldipine and by 80% and 47%, by co-administration of nicardipine. The mean Cmax and AUC of nifedipine are increased by 64% and 79%, respectively, by co-administration of propranolol.

Propranolol does not affect the pharmacokinetics of verapamil and norverapamil. Verapamil does not affect the pharmacokinetics of propranolol.

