### Cardiovascular Drugs

#### Antiarrhythmics

Propafenone has negative inotropic and beta-blocking properties that can be additive to those of propranolol. Quinidine increases the concentration of propranolol and produces greater degrees of clinical beta-blockade and may cause postural hypotension. Amiodarone is an antiarrhythmic agent with negative chronotropic properties that may be additive to those seen with  $\beta$ -blockers

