### Calcium Channel Blockers

Caution should be exercised when patients receiving a beta blocker are administered a calcium-channel-blocking drug with negative inotropic and/or chronotropic effects. Both agents may depress myocardial contractility or atrioventricular conduction.

There have been reports of significant bradycardia, heart failure, and cardiovascular collapse with concurrent use of verapamil and beta-blockers.

Co-administration of propranolol and diltiazem in patients with cardiac disease has been associated with bradycardia, hypotension, high-degree heart block, and heart failure.

There have been reports of significant bradycardia, heart failure, and cardiovascular collapse with concurrent use of verapamil and beta-blockers.

Co-administration of propranolol and diltiazem in patients with cardiac disease has been associated with bradycardia, hypotension, high-degree heart block, and heart failure.

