### Neuroleptic Drugs

Hypotension and cardiac arrest have been reported with the concomitant use of propranolol and haloperidol.

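### As extracted, exclusion I leaves out verapamil and haloperidol, although Section 7 reports cardiovascular collapse or cardiac arrest when they are combined with beta-blockers or propranolol; adding them is a cheap precaution.

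*Combined protocol and SAP*

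**What the plan says.** Section 5, exclusion I, opens with "I) Patients taking any of the following medications will be excluded". As extracted, three items follow: beta-blockers as a class, amiodarone and sotalol. Exclusion G separately bars current treatment with a beta-adrenergic antagonist. Exclusion B bars cardiac disease, including A-V block and any arrhythmia or bradycardia, and inclusion G requires a normal baseline EKG. Hypertension is not an exclusion; inclusion E accepts a diastolic pressure of up to 95 mmHg.

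Section 7 gives these warnings for the two drugs:

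- Calcium Channel Blockers: "There have been reports of significant bradycardia, heart failure, and cardiovascular collapse with concurrent use of verapamil and beta-blockers". The same part advises caution with calcium channel blockers that have negative inotropic or chronotropic effects.
- Neuroleptic Drugs (under the precautions): "Hypotension and cardiac arrest have been reported with the concomitant use of propranolol and haloperidol".

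The contraindications in Section 7 read "Propranolol is contraindicated in 1) cardiogenic shock; 2) sinus bradycardia and greater than first degree block; 3) bronchial asthma", followed by known hypersensitivity. Neither verapamil nor haloperidol appears there.

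Section 6 sets the dose at 1.5 mg/kg/day in two daily doses, with a taper at the end and no upward titration described. Section 8 states that the dose is not modified.

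**The concern.** The exclusion list is the plan's explicit means of keeping interacting drugs away from propranolol. Followed exactly, it admits patients on two drugs for which the protocol's own drug section reports collapse or arrest in combination. Section 7 advises caution with calcium channel blockers of this kind and, under General dosing, says that dose should be tailored to response. Here the dose is set by weight and is not adjusted, so the most direct point at which to act on the warnings is before the first tablet.

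The later safeguards in Section 8 are the call 4 to 6 hours after the first dose, twice-daily home blood pressure and pulse, and the stopping rules (below 100/60, pulse under 55, or an adverse event of grade 2 or more). All of these act after exposure. Section 6 places the first dose on the morning after dispensing, which suggests home, although it also says that the drug is administered at the baseline visit, so the setting is not fully settled. At stake is avoidable serious risk in a short pre-surgical study with a biological primary endpoint.

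**Working it through.** The plan gives no figure on this point, so the main check sets its texts side by side.

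**1. Does the list cover the two drugs?** Of the three items in exclusion I, none is verapamil or haloperidol, and neither drug belongs to the one class named (beta-blockers). Nothing else in Sections 5, 6 or 8 prohibits either.

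**2. Are the warnings limited to patients already excluded?** The verapamil and haloperidol sentences carry no such limit. The diltiazem sentence in the same part of Section 7 is limited to patients with cardiac disease, whom exclusion B is meant to remove, so diltiazem is not part of this point.

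**3. Would another entry check stop such a patient?** Section 6 provides a chart review: "Study staff will also conduct a chart review to gather" the medical history. In Section 8 a cardiologist "will review the history and physical exam data, and the EKG to assure that the patient is unlikely to have pre-existing cardiac disease". With exclusion B and the EKG, these checks look for heart disease. They will remove some verapamil users, namely those treated for a cardiac condition. They do not require removal of a patient who takes verapamil for blood pressure, or who takes haloperidol, and whose heart is normal. Exclusions G and I do imply a look at current medicines, but neither drug is on the list being looked for.

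**4. How does the plan treat a comparable drug?** Amiodarone is excluded although it is not among the listed contraindications. Section 7 gives two grounds. One is pharmacodynamic: "Amiodarone is an antiarrhythmic agent with negative chronotropic properties that may be additive to those seen with" beta-blockers. The other is pharmacokinetic: the Cytochrome P-450 paragraph names amiodarone among CYP2D6 substrates or inhibitors that may raise propranolol levels or toxicity. For verapamil there is no second ground of this kind: "Verapamil does not affect the pharmacokinetics of propranolol". The outcomes reported for verapamil and haloperidol are, however, graver than those stated for amiodarone. The plan has thus already gone beyond the contraindications as a precaution.

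**5. Exposure, under an assumed prevalence.** Let p be the share of otherwise eligible patients taking either drug. The documents do not give p; 0.5%, 1% and 2% are assumptions. The planned enrolment is n = 30 (Sections 6 and 9).

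| p | At least one user: 1 − (1 − p)^30 | Expected users: 30p | Extra otherwise eligible patients screened to enrol 30: 30p/(1 − p) |
|---|---|---|---|
| 0.5% | 1 − 0.995^30 = 0.140 | 0.15 | 0.15/0.995 = 0.151 |
| 1% | 1 − 0.99^30 = 0.260 | 0.30 | 0.30/0.99 = 0.303 |
| 2% | 1 − 0.98^30 = 0.455 | 0.60 | 0.60/0.98 = 0.612 |

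These are chances of enrolling a user, not of harm. Converting them to harm would need an event rate, which the documents do not contain.

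**The case against.** The strongest reply is that the documents ask for caution with calcium channel blockers, not exclusion. Neither drug is a contraindication, and the haloperidol sentence says only that events have been reported, with no dose, route or frequency. That stands, and it sets the weight of the point. A reader might infer that the plan breaches a stated contraindication; the documents do not support that.

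A second reply is that the choice of two drugs is selective. Section 7 also warns about reserpine, digitalis, quinidine and thioridazine without limiting the warnings to cardiac patients. This has some force. The working line is the severity of the outcome named: collapse and arrest, as against bradycardia, syncope, postural hypotension or raised drug levels. The investigators may reasonably consider the others too.

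Third, the dose is not unusual. At assumed weights of 60, 80 and 100 kg, 1.5 mg/kg/day is 90, 120 and 150 mg/day, against a usual hypertension start of 80 mg/day (40 mg twice daily) and maintenance of 120 to 240 mg/day in Section 7. That is correct. The point rests on the combination and on the absence of dose adjustment, not on the dose being high. Nor do the documents say when after dosing such events occur, so it cannot be claimed that they would precede the telephone call.

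Three further stronger readings should be resisted. One is that the plan has no medicines check at all: exclusions G and I cannot be applied without one, and the case report forms are not among the documents. Another is that naming the drugs at entry prevents the exposure: a criterion acts only at entry, and a drug may be started later. The third is that amiodarone is excluded on weaker grounds throughout: it has the CYP2D6 ground that verapamil lacks.

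Finally, the list may be incomplete as extracted. A stray word (Input) sits directly above it, and exclusion D is missing from the lettering. That possibility is open and has to be settled first.

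**Conclusion.** The point holds as a low-cost safety improvement that should be made, with medium confidence. It depends on the list being complete as extracted. If a lost item covers both drugs, the exclusion part falls away, and only the advice to re-check medicines during dosing remains.

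The size of the residual group is unknown. Under the assumed 0.5% to 2% use, fewer than one user is expected among 30; true use could be lower still once exclusion B has acted. A reader might take the 14% to 45% range as a risk of collapse or arrest. It is not, and no such risk can be computed from the documents. The case for the change rests on the severity of the outcomes that the protocol itself reports, on a dose that is not adjusted, and on the small effort needed.

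**What to change.** 1. Check the source file for a list item lost at the stray word above exclusion I or at the missing exclusion D.
2. If neither drug was covered there, add verapamil and haloperidol to exclusion I.
3. Check for both in the medicines review that exclusions G and I already require, before dispensing, and ask again at the existing contacts (the call after the first dose and each visit), recording the answer in REDCap. Refer any user found during dosing to the principal investigator and co-investigators, who under Section 8 already decide whether treatment continues.

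The cost is two drug names in one criterion and one question at contacts that already take place. The downside is a slightly narrower eligible population. Because the exclusion acts before enrolment, the target of 30 is unchanged; at the assumed prevalences, fewer than one additional otherwise eligible patient would need to be screened.

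### Exclusion J counts three weeks from biopsy rather than from first dose, so it does not ensure that an eligible patient can finish propranolol before surgery

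*Combined protocol and SAP*

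**What the plan says.** Section 5, exclusion J, is the only eligibility rule on time to surgery: "If patient is scheduled to receive surgery in less than 3 weeks of biopsy, then patient will not be eligible". Its clock starts at biopsy. The inclusion criteria in the same section admit patients diagnosed up to 90 days earlier.

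Section 6 (Investigational Plan) starts treatment after eligibility and signed consent, and the "first dose will be in the morning the day after the study medication is distributed to them". It describes the opportunity as a window that also runs from diagnosis to surgery: "it is imperative that we catch patients in the 3 week window from when the patient is diagnosed with breast cancer".

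On duration, section 6 says: "Participants will remain on 1.5 mg/kg/day of Propranolol, which will be taken twice daily, for 2 weeks and 4 days". The taper follows in two steps: "The patient will be asked to start a tapering period on day 5 of week 2 and their dose will be lowered by 50" per cent, and then "On day one of week 3, patients will be asked to lower their dose again by 25% of their original dose", held for four days, after which the drug stops. Section 8 (Toxicity Monitoring and Dose Modification) says: "Study treatment will continue 25 days until there is an unacceptable toxicity".

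Section 9 makes the change in tumor proliferative index the primary endpoint. Under section 4, the post-treatment Ki-67 is read on the surgical specimen.

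**The concern.** The rule that is meant to secure the treatment window starts on one date and the treatment starts on another. Time spent on consent, baseline assessment and dispensing comes out of the 21 days. No section sets a minimum interval from consent, dispensing or first dose to surgery, or says that surgery will be timed to fit the course. The course length is itself unclear, so it is not possible to say how far exclusion J falls short without first choosing a reading.

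The endpoint is a within-patient change in a single arm. If some patients are operated on at full dose, some in mid-taper and some after stopping, the mean change can combine different exposures, and there is no control group against which to separate them. An early operation also cuts off the planned taper, which section 6 supports with a reference on beta-blocker withdrawal. The plan does not say what happens to doses left at surgery.

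**Working it through.** **Inputs.** Minimum biopsy-to-surgery interval: 21 days (section 5, J). Full dose 1.5 mg/kg/day, the 18-day phrase (2 × 7 + 4) and the taper steps: section 6. Stated duration 25 days: section 8. Assumptions: no dose on the day of surgery (if one is taken that morning, one more day is available), and the last step is 25% of the original dose (50% less 25%).

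**The plan's own figure.** Section 8's 25 days can be reproduced from section 6 by counting weeks as completed weeks. Day 5 of week 2 is then 14 + 5 = day 19, and day 1 of week 3 is 21 + 1 = day 22. That gives 18 days at full dose, 3 at half dose and 4 at the last step: 18 + 3 + 4 = 25.

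**The other reading.** By ordinary week counting, day 5 of week 2 is 7 + 5 = day 12 and day 1 of week 3 is 14 + 1 = day 15. The drug stops after day 18: 11 + 3 + 4 = 18 days, which is exactly two weeks and four days, taper included.

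**Planned dose in full-dose days.**
- 25-day reading: 18 + 3 × 0.5 + 4 × 0.25 = 20.5, or 20.5 × 1.5 = 30.75 mg/kg.
- 18-day reading: 11 + 1.5 + 1 = 13.5, or 13.5 × 1.5 = 20.25 mg/kg.

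**Fit at exclusion J's limit.** Let d be the days from biopsy to first dose. With surgery on day 21, the dosing days available are 21 − d. A course of D days needs d + D days from biopsy to surgery. The values of d are assumptions, because the documents give no biopsy-to-consent times.

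| d | Days available | 25-day: short by | 25-day: dose received | 18-day: short by | 18-day: dose received | Interval needed (25 / 18) |
|---|---|---|---|---|---|---|
| 1 | 20 | 5 | 19/20.5 = 93% | 0 | 100% | 26 / 19 |
| 3 | 18 | 7 | 18/20.5 = 88% | 0 | 100% | 28 / 21 |
| 4 | 17 | 8 | 17/20.5 = 83% | 1 | 13.25/13.5 = 98% | 29 / 22 |
| 7 | 14 | 11 | 14/20.5 = 68% | 4 | 12.5/13.5 = 93% | 32 / 25 |

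The 25-day course does not fit even at d = 0, since 25 > 21. The 18-day course fits when d + 18 ≤ 21, that is, d ≤ 3. Full-dose days are lost only when 21 − d < 18 (d > 3) on the 25-day reading, or when 21 − d < 11 (d > 10) on the 18-day reading.

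**Late enrolment.** For illustration, suppose drug is dispensed on day 60 after biopsy, the first dose is on day 61 and surgery is on day 65. Exclusion J is met (65 ≥ 21), yet only 65 − 61 = 4 dosing days are available.

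**The case against.** The best defence is that exclusion J is a floor and not a schedule, and that short lags do little harm. On the 18-day reading nothing is lost up to a 3-day lag, and 93% of the planned dose is still received at 7 days. On the 25-day reading a lag of up to 3 days costs taper doses only. This stands, and it limits the size of the point. The 18-day course also sits naturally within section 6's three-week window, which suggests that early enrolment is intended. The criteria nevertheless permit late enrolment, and nothing requires a first dose within 3 days.

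The medication diary, the REDCap record, adherence as Aim 3 and the 20% dropout allowance would let exposure be described afterwards. They do not enforce an interval.

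A reader might infer three stronger claims that the documents do not support:

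- **A built-in two-week delay.** Inclusion D restricts alcohol, illicit drugs and caffeine "for at least two weeks before and during the treatment period". It is worded as a medical ability to comply. No run-in is scheduled, and section 6 begins treatment once consent is signed, so no delay should be charged to the plan on this account.
- **That 25 days is the settled duration.** Section 8 and the 18 + 3 + 4 count favor it; ordinary week counting and the match with the 18-day phrase favor the other. The text leaves it open.
- **That the short plasma half-life (3 to 6 hours, section 7) is a reason to complete the taper.** Patients who finish are sampled on no drug, whereas one operated on in mid-taper has more drug on board. The half-life therefore does not show that losing taper days harms the Ki-67 endpoint.

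**Conclusion.** The point holds. As written, exclusion J admits patients who cannot finish the 25 days stated in section 8 at any lag, and patients who cannot finish the 18-day reading of section 6 once the first dose comes 4 or more days after biopsy. The first statement needs no assumed lag; the second assumes no dose on the day of surgery (with one, the limit moves by a day). At short lags the loss is mainly taper doses. A material loss of full-dose treatment needs surgery near the 21-day floor together with a lag above 3 days (25-day reading) or above 10 days (18-day reading), or else late enrolment with surgery soon after.

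The documents give no distribution of intervals. Neither the number of patients affected nor the effect on the Ki-67 estimate can be computed, and the point should not be read as showing that the estimate is biased by any particular amount. It is still more than a missing detail, because a stated eligibility rule does not secure the planned treatment. It should be amended.

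**What to change.** 1. State one course length in numbered study days and make sections 6 and 8 agree. If 25 days is meant: full dose on days 1–18, half dose on days 19–21, last step on days 22–25. If 18 is meant: days 1–11, 12–14 and 15–18.
2. Reword exclusion J so that surgery is scheduled no earlier than that number of days (25 or 18) after the planned first dose, and align section 6's three-week window with it.
3. Record days from first dose to surgery and from last dose to surgery, and report both beside the Ki-67 change. A minimum interval alone does not make time off drug uniform.

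The cost is a wording amendment to sections 5 and 6 (and to section 8 if 18 days is meant), plus two derived intervals from data that the diary and REDCap already capture. Some patients with short windows will be screened out and accrual may slow slightly. With a 1-day lag, the interval from biopsy to surgery must be at least 26 days for the 25-day course. For the 18-day course it is 19 days, which exclusion J already covers.
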